2.4.4 MY AGILE HEALTH PROFILE

As a reminder text messages will only be delivered for 6 months to participants. AgileHealth profiles are created for ALL patients who are enrolled in the program.

Visit the following link admin.agilehealth.com to create an AgileHealth patient profile:

- Enter your username and password to login.
- Enter the program code 'USCDBRCT' and click on Enroll Now. Make sure to turn off Pop-Up Blockers or you will not be able to proceed.
- Fill out the first section labeled 'About Me'. Enter the patient's information and corresponding Study ID assigned in RedCap. Be diligent and make sure all information is correct and click on 'Continue'.
- Next, complete the section labeled 'My Account'. Use the same e-mail provided in RedCap. If patient does not have an e-mail, use the e-mail created when completing the RedCap survey and click on 'Continue'.
- Fill out the 'My Health' section. Since you are enrolling the patient, click on patient. You will need the patient to provide the first name of their potential supporter during this step and log it in the appropriate space. Click on 'Continue'.
- Finally, complete the 'Preferences' section. Select the language the patient prefers to receive their messages in and select the start date for the program.
 - The healthy start date is the first Monday that is three weeks after patient enrollment.
- Click on User Agreements and complete enrollment.
- **IMPORTANT:** Patient must respond 'Yes' to an automated text message sent to their phone after enrolling them in the AgileHealth. If they do not respond 'Yes', then enrollment is not complete.
 - If they do not receive a message then they may have a block by their carrier. Follow the instructions on the Block Lift PDF to lift the block.

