### **Study Objectives:**

#### Primary Objective:

1. Examine the change in percent glycosylated hemoglobin at 6 months for FANS supported patients vs non-augmented support patients.

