#### Enrollment & Randomization

The goal of this investigation is to study augmenting existing social support via mHealth, so patients were only eligible to be enrolled in the study if a supporter agreed to participate as well; however, this took up to three weeks to contact and enroll the supporter. Given the potential lag, all potentially eligible patients were registered in the SHERPA platform used by Agile Health while in the ED. Occasionally, patients lacked cellular service in the ED and were not able to text-in the Federal Communications Commission-required YES message to opt in during their initial ED visit; we texted and called these patients daily for up to one week until they texted back in YES. The supporter was not contacted until after the patient was fully registered in the system. If a supporter was not eventually enrolled as well, the patient still received the patient text-messaging program, however they were removed from further participation in the study.

Supporters were enrolled either in the ED during the initial contact with the patient or remotely by telephone if they were not present in the ED. Each patient was instructed to rank up to three family or friends who would provide them the most support. As the intervention encourages communication between a patient and a supporter, only one supporter was enrolled per patient to not overwhelm patients with suggestions for healthy living from multiple loved ones. We collected multiple contact numbers for each potential supporter from each patient. We called daily for up to three weeks to enroll supporters.

Enrolling supporters consisted of verbal consent, confirming age>18 and the ability to send and receive text messages, completion of supporter survey instruments and registration in the

SHERPA platform. Registration in the SHERPA system required a YES text back from the supporter. If the supporter did not respond with the required text-in YES message, we called them daily to remind and assist them with completing registration. After supporter enrollment was completed, the dyads were randomized to the FANS mHealth-augmented social support or pamphlet-based social support education for the supporter. All patients received the TExT-MED patient program.

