## **Statistical Analysis**

### Primary and Secondary Outcomes

The primary outcome in this trial is the change in A1C from baseline to six-months, with a priority secondary outcomes of change in A1C from six to twelve months, with the exposure of interest of TExT-MED+FANS.

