## **Hypothesis Analysis**

Initial changes in outcomes (primary and secondary) will be compared between groups with paired t-tests. This will be followed by a longitudinal method with a mixed effects regression model to account for correlated outcome data (zero-six month and six-twelve month changes) and loss to follow up. Analyses will be conducted by intent-to-treat, with participants analyzed according to their randomized intervention regardless of adherence.

Because change in A1C is the outcome, participants who drop out prior to six-months will not be included in the analysis. All participants who complete the twelve-month study will provide two outcome measures of six-month change: a zero-six month measure of treatment efficacy, and a six-twelve month measure of sustainability of treatment effect. The linear mixed effects model will include a random intercept term for participants. Fixed effects will include treatment allocation, initial level of A1C (zero month measure for treatment efficacy, six-month measure for sustainability), and a covariate of study period (zero-six month, six-twelve month). The main effect of treatment will test for group differences over both zero-six and six-twelve month periods. An interaction term of treatment by study period will test for differences in treatment effects by study period; treatment effects will be estimated and tested for differences by study period in this interaction model. Model assumptions including normality of model residuals and homogeneity of variance will be evaluated. A sensitivity analysis confined to adherent participants (those who have not opted out of messages and have received 75% or greater of messages confirmed by message delivery platform) will be conducted. Mixed effects linear regression models will be conducted on secondary outcomes as detailed above.

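### The SAP does not say which analysis decides the primary 0-6 month A1C question, and its only unambiguous model-based treatment test covers both the 0-6 and 6-12 month periods

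*SAP*

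**What the plan says.** The endpoint is clear. SAP, Primary Objective: "Examine the change in percent glycosylated hemoglobin at 6 months for FANS supported patients vs non-augmented support patients". SAP, Primary and Secondary Outcomes: "The primary outcome in this trial is the change in A1C from baseline to six-months", with "priority secondary outcomes of change in A1C from six to twelve months" placed second.

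SAP, Hypothesis Analysis, then describes three analyses that bear on that endpoint:

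1. A t-test: "Initial changes in outcomes (primary and secondary) will be compared between groups with paired t-tests".
2. A mixed model on the two six-month changes, with treatment, the A1C level at the start of each period and study period as fixed effects, and a random intercept for participant. Of this model it says: "The main effect of treatment will test for group differences over both zero-six and six-twelve month periods".
3. The same model with a treatment-by-period term, where "treatment effects will be estimated and tested for differences by study period in this interaction model".

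The mixed model comes after the t-test, but only the analysis of adherent participants is given a rank (sensitivity). The supplied text states no alpha, hierarchy or multiplicity rule.

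**The concern.** A primary endpoint needs one named test. Here the candidates do not all address the same quantity. The pooled main effect brings the secondary 6-12 month period into the comparison, so it can miss a real six-month effect or report an effect when there was none at six months. The sentence on the treatment-by-period model can be read in two ways: as a test of the treatment effect within each period, or only as a test that the two effects differ. On the second reading no model-based test of the 0-6 effect against zero is specified. The t-test cannot be run as worded, because the two arms are independent patients and a paired test does not compare them.

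At stake is whether the reported primary result answers the primary question, and whether the choice of result is fixed before the data are seen.

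**Working it through.** There is no stated sample size, power or alpha to reproduce. The check is algebra followed by simulation on assumed inputs.

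**What the pooled coefficient estimates.** Take equal variances, exchangeable correlation r between visits, full retention and balanced baselines. The slope of change on initial level is then r-1 in both periods.

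- 0-6 months: adjusted effect = d6.
- 6-12 months: adjusted effect = (d12 - d6) - (r-1)d6 = d12 - r·d6. The covariate here is the six-month A1C, which treatment may already have changed.
- Pooled: [d6 + d12 - r·d6]/2 = [d12 + (1-r)d6]/2.

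This equals d6 only if d12 = (1+r)d6, that is, only if the arm difference keeps growing after month 6. With d6 = 1.0 and a sustained effect (d12 = 1.0), it is (1 + 0.7)/2 = 0.85, (1 + 0.5)/2 = 0.75 and (1 + 0.3)/2 = 0.65 at r = 0.3, 0.5 and 0.7.

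**Simulation.** Assumed: SD 2 at every visit, d6 = 1.0 unless stated, two-sided 5%, equal arms, no dropout, and n chosen for about 80% power on the 0-6 contrast. The t-test is read as two-sample.

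| | r = 0.3 | r = 0.5 | r = 0.7 |
|---|---|---|---|
| n per arm | 59 | 49 | 34 |
| Pooled coefficient (formula), sustained | 0.85 | 0.75 | 0.65 |
| Same, half faded (d12 = 0.5) | 0.60 | 0.50 | 0.40 |
| Same, fully faded (d12 = 0) | 0.35 | 0.25 | 0.15 |
| Pooled power, sustained | 93% | 87% | 77% |
| Pooled power, half faded | 68% | 51% | 32% |
| Pooled power, fully faded | 29% | 16% | 6% |
| Pooled test and 0-6 contrast disagree, sustained | 17% | 17% | 21% |
| No effect: at least one of three tests significant | 10.5% | 9.1% | 8.2% |

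- The 0-6 contrast held 79-81% power throughout, with type I error of 4.6-5.4%.
- With d6 = 0 and d12 = 1.0 the formula gives 1.0/2 = 0.50 at any r, and the pooled test rejects in about 50% of trials.
- With 30% lost after month 6, pooled power when fully faded is 39% / 27% / 16%. With correlation that decays over time (AR(1)) it is 29% / 18% / 9%.
- Repeat runs with least-squares fits in place of the mixed model agreed closely; the sustained disagreement was then 17-22%.

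**Dependence on sample size.** The disagreement rate for a sustained effect follows from setting n for 80% power. At r = 0.5 it falls to about 7% at 75 per arm and under 1% at 150.

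**Which tests count.** Counting only the two model-based tests, the chance under no effect that either is significant is about 6.5-8%.

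**The case against.** The strongest reply is that the plan already supplies most of the answer. The endpoint is fixed, the SAP labels the 0-6 period efficacy and the 6-12 period sustainability, and no sentence assigns the pooled effect to the primary hypothesis. The treatment-by-period model yields the 0-6 estimate. The sentence about it would be partly redundant if it meant only the interaction test, so period-specific testing is a natural reading. This stands as far as it goes: a suitable analysis is within the plan, and one should not infer that the 0-6 effect will go untested. But even if the mixed model is taken as the main analysis because it follows the t-test, the choice between its pooled effect and its 0-6 contrast stays open.

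Three stronger readings are tempting and not supported.

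- *The pooled test will lose power because the effect will fade.* Protocol 2.4.4 says "text messages will only be delivered for 6 months to participants", but the SAP adds "All patients received the TExT-MED patient program", so the end of patient messages affects both arms. Protocol 2.3.2 and 2.5 imply that supporter messages run alongside the patient's six months. That makes fading plausible without establishing it. With a sustained effect, pooled power is near or above 80%.
- *The trial's false-positive rate is 8-11%.* That figure needs a rule allowing success on any significant test, and a t-test corrected to two-sample. No such rule is stated.
- *The tests would disagree in about one trial in five or six.* That holds only near 80% power, and the documents give no N.

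The formula also idealises. Eligibility at A1C of 8.5 or above truncates the baseline. With an assumed untruncated mean of 9 and SD of 2, the sustained coefficient becomes 0.88 / 0.78 / 0.70, and at r = 0.7 pooled power (83%) is no longer below that of the 0-6 contrast (82%). The gap narrows but remains.

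**Conclusion.** The point holds as a failure to designate the deciding test, made worse by a mismatch: the only unambiguous model-based test of treatment is not a test of the primary effect. That the targets differ follows from the SAP's own wording and needs no assumed number. The sizes do depend on assumptions about SD, r, n, retention and the course of the effect after month 6. Under those used here, the shortfall in the coefficient is 15-35% for a sustained effect. The serious losses of power arise only if the arm difference fades, and the spurious rejections only if a difference emerges after month 6. The multiplicity figures show what an open choice could cost; they are not properties of the plan. This should be fixed, and it can be fixed within the analyses already planned.

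**What to change.** In SAP, Hypothesis Analysis:

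- Name the 0-6 month treatment contrast from the planned treatment-by-study-period model as the single primary test, and state its alpha and sidedness.
- Label the pooled main effect and the 6-12 month contrast secondary. Reconcile the latter with the first item under Secondary Objectives, which refers to change at 12 months, whereas Primary and Secondary Outcomes refers to change from six to twelve months.
- Reword the interaction sentence so that tests within each period are distinguished from the test that the periods differ.
- Replace *paired* with two-sample and label that t-test supportive.

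The cost is a few sentences, with no new data and no new model. The statistical price is some power given up against pooling if the effect persists: about 80% against 87% at r = 0.5, and 80% against 93% at r = 0.3, under the assumptions above.

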### **Planned Subgroup Analysis:**

To determine if subgroups of participants are differentially affected by the intervention, secondary analyses evaluating intervention moderators are planned. For A1C and each of the secondary outcomes, interaction terms (randomized intervention-by-moderator product terms) will be added to the mixed effects linear models described above. Variables evaluated as moderators will include gender, language preference, years with diabetes, baseline frequency of mobile usage, physical proximity to supporter, baseline social connectedness, and baseline support. If any of these factors indicate significant moderation, intervention effects will be estimated by levels of the moderator. Secondary analyses of the primary A1C outcome will use structural equation modeling to evaluate the secondary behavior and efficacy outcomes as mediators of the TEXT-MED+FANS intervention. Initial analyses will evaluate the associations of changes in behavior and efficacy variables with change in A1C using mixed effects models as detailed above. The A1C mediating model will then include randomized intervention, baseline A1C, any moderating variables detected above, and change in a behavior or efficacy outcome as a possible mediator. Mediation will be tested with bootstrapped samples, evaluating the direct and indirect (mediated) effects of changes in behavior and efficacy outcomes. The final model will include significant moderators and mediators of the TEXT-MED+FANS effect on A1C.

Additionally, after completion of enrollment, substantial differences in baseline support and contact between patients and their selected supporters became evident, as some supporters took up to three weeks to enroll. We now plan on conducting a sub-analysis based on

supporter immediate availability for enrollment versus delayed enrollment.

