#### Social support measures:

Diabetes-related supportive and obstructive family behaviors are measured by patient report on the Diabetes Family Behavior checklist. Family behaviors: supportive and non-supportive sub-scores of the Diabetes Family Behavior Checklist: supportive ranges from 4-45, non-supportive ranges from 7-35.

Diabetes-specific social support is measured by the Diabetes Care Profile Support Questions, with sub-scores for perceived disease specific support needs and perceived disease specific support received. Diabetes Care Profile support questions: Support wanted, and support received. Each range from 5 to 30, high scores indicating high desire for support and higher support received.

General social support is captured by the Norbeck Social Support Questionnaire Emotional and Tangible subscales. General social support: Norbeck Social Support Questionnaire, emotional sub score (ranges 0-16, with higher scores indicating higher perceived emotional support) and tangible sub score (0-8, higher score indicating higher perceived tangible support). While the

sub scores are highly correlated, the authors do not recommend Cronbach's alpha as a test of internal validity. However the Pearson correlations between the emotional support items was 0.96 and the tangible support items was 0.89.

(<http://eileengigliotti.com/uploads/1/1/0/2/110241155/nssq-psychometric.pdf>)

Supporter diabetes-related distress is measured by response to the Partner Distress Scale, which was initially developed for partners of patients with type 1 diabetes, but is used in this expanded support context with permission of the scale author. The self-report scale consists of 21 items in four domains: "my partner's diabetes management", "how best to help", "diabetes and me", and "hypoglycemia". The Cronbach's alpha was 0.76. It has not been previously validated in Spanish speaking population. For this study, the scale was translated and back translated by separate 2-person native Spanish speaking teams. Greater partner distress is correlated with higher A1C among patients and worse self-care, as is lower satisfaction with relationship with the partner

Report of frequency of patient-supporter contact and proportion of communication that is about diabetes is collected from the patients and confirmed by collecting this information from the supporter as well.

Potential modifiers at baseline

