Mobile technology use: Mobile technology use will be measured by questions modeled after the Pew Hispanic Center survey with the addition of questions about frequency of contact between the patient and supporter, and the proportion of communication that is about diabetes. Supporter mobile usage is also captured with the Pew questions.

Health literacy: Health literacy is measured by the Brief Health Literacy Screen developed by Chew, et al. This screen has been validated in English and Spanish speakers.

Age: collected from medical records

Ethnicity: Collected by patient self-report, with option for decline to state

Race: collected by patient self-report, with option for more than one race and decline to state

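### Seven moderators are tested on A1C and every secondary outcome with no stated alpha, error control or exploratory label, significance decides what is estimated and modelled, and the SAP's two moderator lists do not match

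*SAP*

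**What the plan says.** The SAP's Planned Subgroup Analysis sets the scope: "For A1C and each of the secondary outcomes, interaction terms (randomized intervention-by-moderator product terms) will be added to the mixed effects linear models described above". It then names the moderators: "Variables evaluated as moderators will include gender, language preference, years with diabetes, baseline frequency of mobile usage, physical proximity to supporter, baseline social connectedness, and". The seventh and last entry is baseline support. The next step depends on the test result: "If any of these factors indicate significant moderation, intervention effects will be estimated by levels of the moderator". The same section feeds any moderators found this way into the mediation model for A1C, and builds the final A1C model from the moderators and mediators that prove significant.

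The measures part of the SAP has a second list, headed "Potential modifiers at baseline". It contains mobile technology use, health literacy ("Health literacy is measured by the Brief Health Literacy Screen"), age, ethnicity and race.

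The subgroup section ends with a further factor that arose once enrollment was complete: "We now plan on conducting a sub-analysis based on" whether the supporter enrolled immediately or later.

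The moderator analyses are called secondary. Neither document, as supplied, states a significance level, a multiplicity adjustment, a testing hierarchy or an exploratory status for them.

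**The concern.** Three features combine.

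- **Number of tests.** Seven moderators crossed with every outcome gives a large family of interaction tests with no error control.
- **Selection by significance.** Passing the test decides which moderators get effects by level and which enter the final A1C model. An interaction that passes at 5% has an estimate at least 1.96 standard errors from zero. The level-specific effects that follow are therefore exaggerated on average, and a chance interaction can become part of the model that summarises the trial.
- **An open family.** The two lists differ, and some moderators have no single measure. Baseline support could be drawn from several sub-scores in the social support section. Social connectedness and physical proximity to the supporter have no named instrument. An analyst could settle the list and the measures after seeing data without departing from the text.

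At stake is the credibility of the subgroup findings and of the final A1C model. The primary comparison of arms is not at stake.

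**Working it through.** The documents give no error rate, sample size or power, so there is no figure of the plan's own to reproduce.

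**Inputs**
- Moderators: 7 (SAP, Planned Subgroup Analysis). Supporter timing would make 8. The union of both lists is 7 + 5 − 1 = 11.
- Outcomes: the SAP gives no count. From its measures sections: 6 self-care subscales + 1 adherence score + 3 utilization measures + 5 psychosocial scales + 6 social support sub-scores = 21, plus A1C = 22.
- Range for the count: 13 (A1C, self-care, adherence and psychosocial scales only) to 30 (22 plus systolic pressure, BMI, weight, abdominal circumference, supporter distress, two contact items and 12-month A1C).
- Alpha: not stated. I assume 0.05 two-sided and also show 0.01.
- One interaction test per moderator and outcome, with no true moderation anywhere.

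**Formulas.** For m tests, the expected number of false positives is m × alpha, whatever the correlation. With independent tests, P(at least one) = 1 − (1 − alpha)^m.

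**Independent tests**

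| Family | m | Expected at 0.05 | P(≥1) at 0.05 | P(≥1) at 0.01 |
|---|---|---|---|---|
| A1C only, 7 moderators | 7 | 0.35 | 1 − 0.95^7 = 30.2% | 6.8% |
| A1C only, 8 | 8 | 0.40 | 33.7% | 7.7% |
| A1C only, 11 | 11 | 0.55 | 43.1% | 10.5% |
| 7 × 13 outcomes | 91 | 4.6 | 99.1% | 59.9% |
| 7 × 22 outcomes | 154 | 7.7 | 99.96% | 78.7% |
| 7 × 30 outcomes | 210 | 10.5 | >99.99% | 87.9% |

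**Correlated tests.** P(at least one) at 0.05 was simulated with 15,000 runs per setting and a common correlation between moderators and between outcomes:

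| Moderator / outcome correlation | 91 tests | 154 tests | 210 tests |
|---|---|---|---|
| 0.3 / 0.3 | 96.6% | 99.4% | 99.9% |
| 0.3 / 0.5 | 92.2% | 97.4% | 98.7% |
| 0.5 / 0.5 | 87.6% | 95.4% | 97.8% |
| 0.5 / 0.7 | 75.6% | 84.0% | 88.6% |
| 0.5 / 0.9 | 52.8% | 57.8% | 61.3% |

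For A1C alone, correlation between moderators lowers 30% to about 27% (correlation 0.3) or 23% (0.5).

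**The two lists side by side**
- Subgroup section: gender, language preference, years with diabetes, mobile usage, proximity to supporter, social connectedness, baseline support.
- Baseline modifier list: mobile technology use, health literacy, age, ethnicity, race.
- Clear overlap: mobile use only. The mobile entry comes "with the addition of questions about frequency of contact between the patient and supporter", which may bear on social connectedness, but the SAP does not say so.

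**The case against.** Testing an interaction before estimating effects by level is the usual guard against naive subgroup claims, and these analyses are called secondary. Both points are fair. Neither controls error over a family of this size, and neither justifies carrying whatever passes into the final A1C model.

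Four stronger readings are tempting, and the documents do not support them.

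- **That non-significant interactions will go unreported.** The rule makes estimation by level conditional on significance. It says nothing about omitting other results, so selective reporting is a risk and not a stated plan.
- **That false subgroup claims are almost certain.** A false-positive test becomes a false claim only if it is presented as a finding. The probability also depends on an alpha and an outcome count that the SAP does not give, and it falls to about 53% in the most favourable 5% setting tried.
- **That all 11 moderators will be tested.** The analysis section names seven. The other list describes how potential modifiers are measured. Its mismatch leaves the family unclear, but the inflation is there with the seven alone.
- **That supporter timing will be passed off as originally planned, or judged by two separate tests.** The SAP says openly when the idea arose. Randomization follows supporter enrollment (SAP, Enrollment & Randomization; Protocol 2.6), so timing is a legitimate pre-randomization factor. The SAP does not say how it will be analysed. The gap is that no interaction is specified for it.

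The measurement ambiguity should not be overstated either. Of the six support sub-scores, non-supportive behavior and support wanted are unlikely readings of baseline support, which leaves about four candidates.

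**Conclusion.** The concern holds in this form. The SAP tests seven moderators on A1C and every secondary outcome without a stated alpha, adjustment or exploratory status. Significance is the gate for level-specific estimates and for entry to the final A1C model, and the moderator list is not reconciled within the document.

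At an assumed two-sided 5% level with no true moderation, the familywise error for A1C alone is about 30% with independent tests, six times nominal. Over 154 tests, 7.7 false positives are expected. At least one is 97% to over 99% likely when outcomes correlate up to 0.5 and moderators up to 0.3. It is about 58% to 84% likely when moderators correlate 0.5 and outcomes 0.7 to 0.9. The outcome count is mine, and the correlations are illustrative. The A1C figure does not depend on the outcome count, and it is the one that bears on the final A1C model.

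This should be corrected, but it concerns secondary analyses. The main treatment test in the SAP's Hypothesis Analysis section is untouched.

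**What to change.** Revise the Planned Subgroup Analysis section of the SAP:

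1. Set one moderator list, reconciled with the list of potential baseline modifiers, and name one baseline measure for each entry.
2. Label all moderator analyses exploratory. Report every interaction estimate with its confidence interval, and the effects by level, whether or not the interaction is significant.
3. Do not let significance alone carry moderators into the final A1C model. If any moderation claim is to be made for A1C, state the alpha and adjust across the list. Holm is one option; with seven moderators at 0.05 its first step is 0.05 / 7 = 0.0071.
4. Analyse immediate versus delayed supporter enrollment by a treatment-by-timing interaction, define the two categories, and list the analysis as added after enrollment.

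The essential changes are the single list, the label, the removal of the gate and the full reporting. The choice of Holm is a matter of preference. The cost is SAP wording, fewer subgroup claims and a longer supplementary table. No new data are needed.

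### In the secondary mediation analysis, the final A1C model keeps only significant moderators and mediators and omits the mediator's baseline value; its treatment term is a direct effect

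*SAP*

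**What the plan says.** The SAP's Primary Objective is to "Examine the change in percent glycosylated hemoglobin at 6 months for FANS supported patients vs non-augmented support patients", and Primary and Secondary Outcomes confirms that "The primary outcome in this trial is the change in A1C from baseline to six-months". Hypothesis Analysis tests this by intent-to-treat in a mixed model with treatment, initial A1C and study period, plus a treatment-by-period interaction. That model contains no mediator and no term chosen by significance.

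Planned Subgroup Analysis then adds two layers.

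- **Moderators.** Seven are tested by interaction terms: "gender, language preference, years with diabetes, baseline frequency of mobile usage, physical proximity to supporter, baseline social connectedness, and baseline support".
- **Mediators.** "Secondary analyses of the primary A1C outcome will use structural equation modeling to evaluate the secondary behavior and efficacy outcomes as mediators". The mediating model contains randomised arm, baseline A1C, "any moderating variables detected above, and change in a behavior or efficacy outcome as a possible mediator". The targets are stated: "Mediation will be tested with bootstrapped samples, evaluating the direct and indirect (mediated) effects of changes in behavior and efficacy outcomes".

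The section's closing rule on this work is: "The final model will include significant moderators and mediators of the TEXT-MED+FANS effect on A1C". The SAP does not say what this model is for, which coefficient will be reported from it, what threshold selects its terms, or what confounding assumption the mediation rests on.

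**The concern.** The rule raises three problems, all within the secondary analysis.

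1. **Selection.** A term that enters only because it was significant has an estimate that is too large on average. Its ordinary interval takes no account of the selection.
2. **No baseline mediator.** The mediator is a change score. Change is negatively correlated with its own starting value through regression to the mean. If the starting level of self-care or self-efficacy also relates to A1C change, leaving it out confounds the mediator path.
3. **Meaning of the treatment term.** Mediators are measured after randomisation. With one in the model, the treatment coefficient is the part of the effect that does not pass through it. If moderator interactions are kept too, the coefficient applies only at the moderators' reference levels.

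At stake is what the trial concludes about how the intervention works: which behaviours carry the effect, and how much of it.

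**Working it through.** The documents give no effect size, standard deviation, alpha or mediated share for this analysis, so there is no figure of the plan's to reproduce. Every input below is an assumption unless a source is named.

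**A. Treatment term with a mediator in the model**

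Inputs: total effect -0.50 A1C points; effect of treatment on the mediator a = 0.5 SD; effect of the mediator on A1C b; residual mediator variance 1; linear model, one mediator, no interaction.

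Formula: direct = total - a × b.

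- b = 0 (no mediation): -0.50 - 0 = -0.50.
- b = -0.50 (half mediated): -0.50 - (0.5 × -0.50) = -0.25.
- b = -1.00 (fully mediated): -0.50 - (0.5 × -1.00) = 0.00.

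Now add an unmeasured common cause with an effect of 0.5 SD on the mediator and 0.75 points on A1C. The estimate of b shifts by 0.5 × 0.75 = 0.375 in size, so the treatment term shifts by 0.5 × 0.375 = 0.19. The shift is upward if the cause moves mediator and A1C in opposite directions, and downward if it moves them in the same direction.

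| True situation | Treatment term, no confounding | With confounding, either sign |
|---|---|---|
| Total -0.50, no mediation | -0.50 | -0.31 or -0.69 |
| Total -0.50, half mediated | -0.25 | -0.06 or -0.44 |
| No effect at all | 0.00 | +0.19 or -0.19 |

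Large-sample simulation agreed with the two rows that have a total of -0.50. Direct plus indirect returned about -0.50 in all scenarios simulated for that sum. The total effect is therefore not lost if both paths are reported.

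**B. Omitting the mediator's baseline value**

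Let M0 and M1 be the mediator at baseline and follow-up, each with variance 1 within arm and correlation r. Let D = M1 - M0. Suppose A1C change = c × T + b × M1 + g × M0 + error, which is the same as c × T + b × D + (b + g) × M0 + error.

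- Cov(D, M0) = r - 1 and Var(D) = 2(1 - r), so their ratio is -1/2 for any r.
- With M0 omitted, the coefficient of D is b - (b + g)/2 = (b - g)/2.
- With M0 included, it is b.

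Take b = -0.50, a = 0.5, c = -0.25 (total -0.50). The true indirect effect is 0.5 × -0.50 = -0.25.

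| g: baseline level on A1C change | Coefficient of D, M0 omitted | Indirect effect (a × coefficient) | Treatment term |
|---|---|---|---|
| +0.50 (only change matters) | -0.50 | -0.25 | -0.25 |
| 0 (only follow-up level matters) | -0.25 | -0.125 | -0.375 |
| -0.50 | 0.00 | 0.00 | -0.50 |
| +1.00 | -0.75 | -0.375 | -0.125 |

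Only the first case is unbiased. The error can go either way. Including M0 returns -0.50 and -0.25 in every row. Simulation at r = 0.3, 0.6 and 0.8 confirmed the first three rows.

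**C. Keeping only significant terms**

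Assume a normal estimate, kept when |z| exceeds 1.96. Let d be the true effect divided by its standard error.

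| d | Chance of being kept | Mean kept estimate ÷ truth | Coverage of the 95% interval, given kept |
|---|---|---|---|
| 0 | 5% | not defined | 0% |
| 0.5 | 8% | 3.99 | 60% |
| 1 | 17% | 2.45 | 84% |
| 2 | 52% | 1.39 | 95% |
| 3 | 85% | 1.09 | 97% |

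Overstatement is present throughout and fades as d grows. Under-coverage is confined to weak effects.

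Chance of at least one false selection at an assumed alpha of 0.05 with independent tests:

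- 7 moderators (SAP list): 1 - 0.95^7 = 30%.
- 8 mediators (assumed: six self-care subscales, medication adherence, self-efficacy): 1 - 0.95^8 = 34%.
- All 15: 1 - 0.95^15 = 54%.

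The mediator figures are closer to a ceiling, because a test of an indirect effect rejects less often than alpha when both paths are null.

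**The case against.** The strongest reply is that this is a mediation analysis doing what such an analysis does. The section calls it secondary, direct and indirect effects are its stated targets, and a direct-effect coefficient is what the model should return. The total randomised effect is already estimated in Hypothesis Analysis. All of this stands.

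A reader might infer something stronger from the words of the rule: that this final model supersedes the Hypothesis Analysis model, so that the trial's reported effect on A1C would be a diluted direct effect. The documents do not support that. No sentence says that the final model replaces the intent-to-treat model or supplies the headline estimate, and its place at the end of the moderator and mediator steps points the other way.

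A reader might also infer that confounding must shrink the effect towards zero. It need not: its sign is unknown, and the opposite sign enlarges the term.

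Nor is it right that nothing is adjusted for. Baseline A1C is in the mediating model, and so are detected moderators. Two candidate moderators are baseline social measures. None of these is the baseline level of the behaviour or efficacy score acting as mediator, and moderators enter only if detected. One could also argue that the covariate list is not meant to be exhaustive. If so, adding the baseline value merely confirms the intention.

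Unmeasured confounding affects any mediation analysis and is not particular to this plan. The baseline mediator is different: a change score requires that it was measured, so leaving it out is avoidable.

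**Conclusion.** The point holds for the secondary mediation analysis only. The primary intent-to-treat effect is untouched.

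Within that analysis, terms kept for significance have overstated effects, and their intervals are too narrow when the true effect is weak. At a true effect of one standard error, the kept estimate averages about 2.5 times the truth and the interval covers 84% of the time. Omitting the mediator's baseline value can halve the estimated mediator effect, remove it, or inflate it, depending on how the starting level relates to A1C change. The final model's treatment term is a direct effect. For an assumed total of -0.50 with no true mediation, confounding of the assumed strength puts it anywhere from about -0.31 to -0.69.

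These sizes rest on assumed effects, variances and alpha, a single mediator, and linear models without interaction. The direction of the selection problem does not depend on those values. The direction of the two confounding problems does.

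This is a cheap improvement of minor severity.

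**What to change.** Replace the final-model sentence in the SAP, Planned Subgroup Analysis, with:

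> The effect of TExT-MED+FANS on A1C is taken from the Hypothesis Analysis model, which has no mediators. Mediation is exploratory: total, direct and indirect effects with bootstrap intervals are reported for every candidate mediator, significant or not, adjusted for baseline A1C and the baseline value of that mediator, with the no-unmeasured-confounding assumption stated. Any model built from significant terms is labelled exploratory, and its treatment term is reported as a direct effect.

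The cost is SAP wording only. No new data are needed, since the baseline scores are already required to compute the changes. The downside is a longer table of exploratory results.
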